5.1.2.1 Hypotheses

If the primary objective is met, non-inferiority of MenACYW conjugate vaccine (Group 1) compared to Nimenrix® (Group 2) in terms of hSBA antibody titers $\geq 1:8$ after a 2-dose series in infants will be tested (Secondary Objective 1).

For each of the 4 serogroups (A, C, W, and Y), the percentages of subjects who achieve an hSBA titer $\geq 1:8$ 30 days after the 2nd dose administered in infancy will be used to compare responses between Group 1 and Group 2 with the following individual hypotheses:

- H_0 (*Null hypothesis*): $p_{(\text{MenACYW})} - p_{(\text{Nimenrix})} \leq -10\%$
- H_1 (*Alternative hypothesis*): $p_{(\text{MenACYW})} - p_{(\text{Nimenrix})} > -10\%$

where $p_{(\text{MenACYW})}$ and $p_{(\text{Nimenrix})}$ are the percentages of subjects who achieve an hSBA titer $\geq 1:8$ in the MenACYW conjugate vaccine group and the Nimenrix® group, respectively.

5.1.2.2 Statistical Methods

Non-inferiority will be demonstrated if all 4 individual null hypotheses (4 serogroups) are rejected. If the lower limit of the 2-sided 95% CI of the difference between the 2 percentages is $> -10\%$, the non-inferiority will be demonstrated. The CI of the difference in percentages will be computed using the Wilson score method without continuity correction.

5.1.3 Statistical Methods for Secondary Objectives 2, 3 and 4

No hypotheses will be tested. Descriptive statistics will be presented.

In general, categorical variables will be summarized and presented by frequency counts, percentages, and CIs. The 95% CIs of point estimates will be calculated using the normal approximation for quantitative data and the exact binomial distribution (Clopper-Pearson method) for proportions. For GMTs and geometric mean concentrations (GMCs), 95% CIs of point estimates will be calculated using a normal approximation assuming they are log-normally distributed.

Objective 2 (Group 3) and objective 4 (Groups 1 and 2)

The meningococcal serogroups A, C, Y, and W measured by hSBA, for Groups 1, 2, and 3, before Dose 1 of MenACYW conjugate vaccine, 30 days after Dose 2 of MenACYW conjugate vaccine in infancy, and before and 30 days after the booster dose (Dose 3) will be described with:

- GMT and 95% CI
- Titer distribution and RCDCs
- Percentage of subjects with titer $\geq 1:4$ and $\geq 1:8$ and 95% CI
- Percentage of subjects with titer ≥ 4 -fold rise from pre-vaccination to post-vaccination, and 95% CI
- Percentage of subjects with hSBA vaccine seroresponse and 95% CI

Objective 3 (Groups 1, 2 and 3)

The antibody titers or concentrations against the antigens of hexavalent vaccine (DTaP-IPV-HB-Hib) will be described:

- At Day 0 (before Dose 1)
 - GMT and 95% CI for Pertussis antigens (pertussis toxin [PT], filamentous hemagglutinin [FHA])
- At 30 days after Dose 2 in infancy
 - GMT and 95% CI
 - RCDCs
 - Percentage of subjects with titer \geq cutoff:
 - Anti-tetanus antibody concentrations ≥ 0.01 IU/mL, ≥ 0.1 IU/mL and ≥ 1.0 IU/mL
 - Anti-diphtheria antibody concentrations ≥ 0.01 IU/mL, ≥ 0.1 IU/mL and ≥ 1.0 IU/mL
 - Anti-poliovirus types 1, 2, and 3 antibody titers $\geq 1:8$
 - Anti-polyribosyl-ribitol phosphate (PRP) antibody concentrations ≥ 0.15 μ g/mL and ≥ 1.0 μ g/mL
 - Anti-hepatitis B surface antigen (HBsAg) antibody concentrations ≥ 10 mIU/mL and ≥ 100 mIU/mL
 - Pertussis vaccine seroresponse for anti-PT and anti-FHA
- Before and 30 days after the booster dose (Dose 3)
 - GMT and 95% CI
 - Titer distribution and RCDCs
 - Percentage of subjects with concentrations/titers \geq cut-off:
 - Anti-tetanus antibody concentrations ≥ 0.01 IU/mL, ≥ 0.1 IU/mL and ≥ 1.0 IU/mL
 - Anti-diphtheria antibody concentrations ≥ 0.01 IU/mL, ≥ 0.1 IU/mL and ≥ 1.0 IU/mL
 - Anti-poliovirus types 1, 2, and 3 antibody titers $\geq 1:8$
 - Anti-PRP antibody concentrations ≥ 0.15 μ g/mL and ≥ 1.0 μ g/mL
 - Anti-HBsAg antibody concentrations ≥ 10 mIU/mL and ≥ 100 mIU/mL
 - Pertussis vaccine seroresponse for anti-PT and anti-FHA

The antibody concentrations against the antigens of PCV10 (Anti-pneumococcal antibody concentrations for serotypes 1, 4, 5, 6B, 7F, 9V, 14, 18C, 19F, and 23F) in Groups 1 and 2, 30 days after Dose 2 in infancy and 30 days after the booster dose (Dose 3) will be described:

- GMT and 95% CI
- Titer distribution and RCDCs
- Percentage of subjects with Anti-pneumococcal antibody concentrations $\geq 0.35 \mu\text{g/mL}$ and $\geq 1.0 \mu\text{g/mL}$

Antibody concentrations against the antigens of PCV13 (Anti-pneumococcal antibody concentrations for serotypes 1, 3, 4, 5, 6A, 6B, 7F, 9V, 14, 18C, 19A, 19F, and 23F) in Group 3, 30 days after Dose 2 in infancy and 30 days after the booster dose (Dose 3):

- GMT and 95% CI
- RCDCs
- Percentage of subjects with Anti-pneumococcal antibody concentrations $\geq 0.35 \mu\text{g/mL}$ and $\geq 1.0 \mu\text{g/mL}$

The Antibody concentrations against the antigens of MMR vaccine 30 days after the MMR vaccine injection^a will be described:

- GMT and 95% CI
- RCDCs
- Percentage of subjects with titer \geq cutoff
 - Anti-measles antibody concentrations (serostatus cutoff: 255 mIU/mL)
 - Anti-mumps antibody concentrations (serostatus cutoff: 10 Mumps Ab units/mL)
 - Anti-rubella antibody concentrations (serostatus cutoff: 10 IU/mL)

5.1.4 Statistical Methods for Secondary Objectives 5 and 6

No hypotheses will be tested. Descriptive statistics will be presented.

^a when the MMR vaccine has been administered concomitantly with the study vaccines

Objective 5 (Group 4)

Antibody titers against meningococcal serogroups A, C, W, and Y measured by hSBA in Group 4 on Day 0 (before Dose 1 of MenACYW conjugate vaccine), 30 days after Dose 3 in infancy, and before and 30 days after the booster dose (Dose 4) will be described with:

- GMT and 95% CI
- Titer distribution and RCDCs
- Percentage of subjects with titer $\geq 1:4$ and $\geq 1:8$ and 95% CI
- Percentage of subjects with titer ≥ 4 -fold rise from pre-vaccination to post- vaccination, and 95% CI
- Percentage of subjects with hSBA vaccine seroresponse and 95% CI

Objective 6 (Group 4)

The antibody titers or concentrations against the antigens of DTaP-IPV-HB-Hib vaccine before and 30 days after the booster dose (Dose 4), the antibody concentrations against the antigens of PCV13 vaccine 30 days after the booster dose (Dose 4), and the antibody concentrations against the antigens of MMR vaccine 30 days after vaccination^a will be described:

- At Day 0 (before Dose 1)
 - GMT and 95% CI for Pertussis antigens (pertussis toxin [PT], filamentous hemagglutinin [FHA])
- 30 days after the booster dose (Dose 4)
 - GMT and 95% CI for all antigens
 - RCDCs for all antigens^b
 - Percentage of subjects with titer \geq cutoff:
 - Anti-tetanus antibody concentrations ≥ 0.01 IU/mL, ≥ 0.1 IU/mL and ≥ 1.0 IU/mL
 - Anti-diphtheria antibody concentrations ≥ 0.01 IU/mL, ≥ 0.1 IU/mL and ≥ 1.0 IU/mL
 - Anti-poliovirus types 1, 2, and 3 antibody titers $\geq 1:8$
 - Anti-PRP antibody concentrations ≥ 0.15 μ g/mL and ≥ 1.0 μ g/mL
 - Anti-HBsAg antibody concentrations ≥ 10 mIU/mL and ≥ 100 mIU/mL
 - Anti-pneumococcal antibody concentrations ≥ 0.35 μ g/mL and ≥ 1.0 μ g/mL for serotypes 1, 3, 4, 5, 6A, 6B, 7F, 9V, 14, 18C, 19A, 19F, and 23F
 - Anti-measles antibody concentrations (serostatus cutoff: 255 mIU/mL)

^a when the MMR vaccine has been administered concomitantly with the study vaccines

^b Including MMR only if MMR vaccine has been administered concomitantly with the study vaccines

- Anti-mumps antibody concentrations (serostatus cutoff: 10 Mumps Ab units/mL)
- Anti-rubella antibody concentrations (serostatus cutoff: 10 IU/mL)
- Pertussis vaccine seroresponse for anti-PT and anti-FHA

The analyses described above include MMR antigens only if the MMR vaccine has been administered concomitantly with the study vaccines.

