9.2.2.2 Immunogenicity Assessment Methods

The immunogenicity assessment methods for the meningococcal serogroups A, C, W, and Y antibody titers for the secondary endpoints are the same as that presented in [Section 9.1.2.2](#).

Antibody responses against the antigens of routine vaccines will also be measured in blood samples (see [Table 9.1](#), [Table 9.2](#), [Table 9.3](#)).

Considering the number of antigens to test, and to mitigate any risk to fail testing in MET58, different profile testing will be performed according to odd- or even-numbered subject ID (ie, different ranking for testing antigens), in case of lower blood volume collected. In the event of insufficient serum sample volume, the immunogenicity assessment method (hSBA assay) for meningococcal serogroups A, C, W, and Y antibody titers will be the prioritized assay. (Refer to [Section 9.1.2.2](#))

^a when the MMR vaccine has been administered concomitantly with the study vaccines

Table 9.1: Blood sampling schedule and testing plan in Groups 1 and 2

Age in months	2 months	5 months	12-18 months	13-19 months
Visit and BL numbers	Visit 1 (pre-vaccination) BL0001	Visit 3 BL0002	Visit 4 (pre-vaccination) BL0003	Visit 5 BL0004
Antigens (Group 1 N= 716 Group 2 N= 716)	Meningococcal serogroups A, C, W, Y Pertussis (PT, FHA)	Meningococcal serogroups A, C, W, Y · Hib (PRP) · Hep B (HBsAg) · Pertussis (PT, FHA) · PCV10 · Poliovirus (types 1, 2, 3) · Diphtheria · Tetanus	Meningococcal serogroups A, C, W, Y · Hib (PRP) · Hep B (HBsAg) · Pertussis (PT, FHA) · Poliovirus (types 1, 2, 3) · Diphtheria · Tetanus	Meningococcal serogroups A, C, W, Y · Measles† · Mumps† · Rubella† · Hib (PRP) · Hep B (HBsAg) · Pertussis (PT, FHA) · PCV10 · Poliovirus (types 1, 2, 3) · Diphtheria · Tetanus
Blood sample volume*	2mL or 3 mL (depending on weight)	3mL or 4 mL (depending on weight)	5mL or 6 mL (for rSBA subset)	5mL or 6 mL (for rSBA subset)

PT: pertussis toxin; FHA: filamentous hemagglutinin; PRP: polyribosyl-ribitol phosphate; Hib: *Haemophilus influenzae* type b; Hep B: Hepatitis B; HBsAg: Hepatitis B surface antigen; PCV10: pneumococcal conjugate vaccine 10-valent.

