*Blood sample volume indicated for BL0001 and BL0002 will be taken from all subjects including those subjects in the rSBA subset, with 2 or 3 mL for BL0001 and 3 or 4 mL collected depending on weight at study visit. The blood sample volume for BL0003 and BL0004 is 5 mL, except for subjects included in the rSBA subset for which blood sample volume is 6 mL. In the rSBA subset, the antibody response to meningococcal serogroups (A, C, W, and Y) will be measured by rSBA assay in addition to hSBA assay (refer to [Section 6.5](#) for more details on the rSBA subset).

†when the MMR vaccine has been administered concomitantly with the study vaccines

For each visit, antigens are listed in descending order of assay priority (highest to lowest priority).

For PCV13: Highest to lowest priority anti-pneumococcal serotypes: 1, 3, 5, 6A, 7F, 19A, 4, 6B, 9V, 14, 18C, 19F, and 23F

Table 9.3: Blood sampling schedule and testing plan in Group 4

Age in months	2 months	7 months	12-18 months	13-19 months
Visit and BL numbers	Visit 1 (pre-vaccination) BL0001	Visit 4 BL0002	Visit 5 (pre-vaccination) BL0003	Visit 5 BL0004
Antigens (Group 4 N= 110)	
 Meningococcal serogroups A, C, W, Y 	
 Meningococcal serogroups A, C, W, Y 	
 Meningococcal serogroups A, C, W, Y Hib (PRP) Hep B (HBsAg) Pertussis (PT, FHA) Poliovirus (types 1, 2, 3) Diphtheria Tetanus 	
 Meningococcal serogroups A, C, W, Y Measles† Mumps† Rubella† Hib (PRP) Hep B (HBsAg) Pertussis (PT, FHA) PCV13 Poliovirus (types 1, 2, 3) Diphtheria Tetanus
Blood sample volume*	2mL or 3 mL (depending on weight)	3mL or 4 mL (depending on weight)	5mL or 6 mL (for rSBA subset)	5mL or 6 mL (for rSBA subset)

PT: pertussis toxin; FHA: filamentous hemagglutinin; PRP: polyribosyl-ribitol phosphate; Hib: *Haemophilus influenzae* type b; Hep B: Hepatitis B; HBsAg: Hepatitis B surface antigen; PCV13: pneumococcal conjugate vaccine 13-valent.

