- 6) For Group 4, antibody titers or concentrations against the antigens of DTaP-IPV-HB-Hib vaccine before and 30 days after the booster dose (Dose 4), antibody concentrations against the antigens of PCV13 vaccine 30 days after the booster dose (Dose 4), and antibody concentrations against the antigens of MMR vaccine 30 days after vaccination^a. The timepoints are:
- Antibody titers or concentrations against the antigens of hexavalent vaccine (DTaP-IPV-HB-Hib)
 - Pre-booster dose:
 - Anti-pertussis antibody concentrations anti-PT, anti-FHA
 - 30 days after the booster dose (Dose 4):
 - Antibody concentrations/titers for all antigens
 - Anti-tetanus antibody concentrations ≥ 0.01 IU/mL, ≥ 0.1 IU/mL and ≥ 1.0 IU/mL
 - Anti-diphtheria antibody concentrations ≥ 0.01 IU/mL, ≥ 0.1 IU/mL and ≥ 1.0 IU/mL
 - Anti-poliovirus types 1, 2, and 3 antibody titers $\geq 1:8$
 - Anti-PRP antibody concentrations ≥ 0.15 μ g/mL and ≥ 1.0 μ g/mL
 - Pertussis vaccine seroresponse for anti-PT and anti-FHA as defined in [section 4.4.2.6](#)
 - Anti-HBsAg antibody concentrations ≥ 10 mIU/mL and ≥ 100 mIU/mL
 - Antibody concentrations against the antigens of PCV13 in Group 4, 30 days after the booster dose (Dose 4):
 - Anti-pneumococcal antibody concentrations for serotypes 1, 3, 4, 5, 6A, 6B, 7F, 9V, 14, 18C, 19A, 19F, and 23F
 - Anti-pneumococcal antibody concentrations ≥ 0.35 μ g/mL and ≥ 1.0 μ g/mL for serotypes 1, 3, 4, 5, 6A, 6B, 7F, 9V, 14, 18C, 19A, 19F, and 23F
 - Antibody concentrations against the antigens of MMR vaccine 30 days after the MMR vaccine injection^a
 - Antibody concentrations for all antigens
 - Anti-measles antibody concentrations (serostatus cutoff: 255 mIU/mL)
 - Anti-mumps antibody concentrations (serostatus cutoff: 10 Mumps Ab units/mL)
 - Anti-rubella antibody concentrations (serostatus cutoff: 10 IU/mL)

^a When the MMR vaccine has been administered concomitantly with the study vaccines

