4.4.2.6 Pertussis vaccine seroresponse for anti-PT and anti-FHA

For Groups 1, 2, and 3, 30 days after Dose 2 in infancy, Pertussis vaccine seroresponse for anti-PT and anti-FHA is defined as:

- If the pre-primary vaccination concentration is $< 4 \times \text{LLOQ}$, post-primary vaccination concentration $\geq 4 \times \text{LLOQ}$
- If the pre-primary vaccination concentration is $\geq 4 \times \text{LLOQ}$, post-primary vaccination concentration \geq pre-primary vaccination concentration

For Groups 1, 2, and 3, before and 30 days after the booster dose (Dose 3) and for Group 4, before and 30 days after the booster dose (Dose 4), Pertussis vaccine seroresponse for anti-PT and anti-FHA is defined as:

- If the pre-booster vaccination concentration is $< 4 \times \text{LLOQ}$, post-booster vaccination concentration $\geq 4 \times$ pre-booster concentration
- If the pre-booster vaccination concentration is $\geq 4 \times \text{LLOQ}$, post-booster vaccination concentration $\geq 2 \times$ pre-booster concentration

4.4.2.7 rSBA Vaccine Seroresponse

rSBA vaccine seroresponse for serogroups A, C, Y, and W is defined as either:

- For a subject with a pre-vaccination titer $< 1:8$, the post-vaccination titer must be $\geq 1:32$;
- For a subject with a pre-vaccination titer $\geq 1:8$, the post-vaccination titer must be at least 4-fold greater than the pre-vaccination titer.

For the vaccine seroresponse evaluated after the last dose in infancy, the post-vaccination titer corresponds to BL0002 (Visit 3 for Groups 1, 2, 3 and Visit 4 for Groups 4) and the pre-vaccination titer corresponds to BL0001 (Visit 1 for all groups).

For the vaccine seroresponse evaluated after the booster dose, two seroresponse indicators will be defined as follows:

- The post-booster vaccination titer corresponds of BL0004 (Visit 5 for Groups 1, 2, 3 and Visit 6 for Groups 4) and the pre-primary vaccination titer corresponds to BL0001 (Visit 1 for all groups).
- The post- booster vaccination titer corresponds of BL0004 (Visit 5 for Groups 1, 2, 3 and Visit 6 for Groups 4) and the pre- booster vaccination titer corresponds to BL0003 (Visit 4 for Groups 1, 2, 3 and Visit 5 for Groups 4).

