5.7 Changes in the Conduct of the Trial or Planned Analyses

The protocol stipulated that "The main immunogenicity analysis will be performed on the PPAS analysis set including PPAS2 for the primary objective and PPAS1 for secondary objective 1 and will be confirmed on the FAS2 and FAS1". However, due to an internal change of analysis process, the main immunogenicity analysis will be confirmed on the FAS2 and FAS1 only if the difference between PPAS1 and FAS1 (or PPAS2 and FAS2) is greater than 10%, as described in [section 5.2.5](#).

Concomitant medications category fields were inactivated, and concomitant medications were coded with WHODrug dictionary by the coding specialists.

Also, as participants in Group 3 and 4 have the same vaccines administered at 2, 4 and at 12 to 18 months of age, actual treatment group derivation for the Safety analysis sets for those groups had been specified in [section 5.2.3](#).

Finally, several analysis cut-offs for some concentrations have been considered in addition to the one already defined in the protocol:

- For anti-diphtheria antibody concentrations, the cut-off ≥ 1.0 IU/mL has been added for secondary objective 3 (30 days after Dose 2) and the cut-off ≥ 0.01 IU/mL has been added for secondary objective 3 (Before and 30 days after the booster dose) and secondary objective 6
- For anti-polyribosyl-ribitol phosphate (PRP) antibody concentrations, the cut-off ≥ 1.0 μ g/mL has been added for secondary objective 3 (30 days after Dose 2)

- For anti-tetanus antibody concentrations, the cut-off ≥ 1.0 IU/mL has been added for secondary objective 3 (30 days after Dose 2) and the cut-off ≥ 0.01 IU/mL has been added for secondary objective 3 (Before and 30 days after the booster dose) and secondary objective 6
- For anti-pneumococcal antibody concentrations for serotypes 1, 4, 5, 6B, 7F, 9V, 14, 18C, 19F, and 23F, the cut-off ≥ 1.0 μ g/mL has been added for secondary objective 3 and secondary objective 6

6 References List

- 1 Newcombe R.G., Two-sided confidence intervals for the single proportion: comparison of seven methods, *Statistics in Medicine*, (1998) 17, 857-872.

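### SAP 5.1.4, Objective 6, lists Group 4 PT and FHA at Day 0, where no pertussis assay is planned, and leaves out the pre-booster time point that endpoint 6 requires

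*SAP*

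**What the plan says.** SAP 5.1.4 opens Objective 6 (Group 4) with its scope: "The antibody titers or concentrations against the antigens of DTaP-IPV-HB-Hib vaccine before and 30 days after the booster dose (Dose 4"), together with PCV13 and MMR antibodies after the booster. The list below it has two time points. The first is "At Day 0 (before Dose 1"), with one item: "GMT and 95% CI for Pertussis antigens (pertussis toxin [PT], filamentous hemagglutinin [FHA"]). The second is 30 days after Dose 4, for all antigens. There is no pre-booster entry.

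Secondary endpoint 6 is set out in SAP 4.2.1.1 and in protocol 9.2.2.1. Both place "Anti-pertussis antibody concentrations anti-PT, anti-FHA" under the pre-booster heading, and neither has a Day 0 pertussis item for Group 4.

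The assay plan is in protocol 9.2.2.2. For Groups 1 and 2, the Day 0 column of Table 9.1 reads "Meningococcal serogroups A, C, W, Y Pertussis (PT, FHA"), and Table 9.2 plans the same for Group 3. In "Table 9.3: Blood sampling schedule and testing plan in Group 4", the Day 0 column holds meningococcal serogroups only.

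**The concern.** The list and the endpoint it is meant to implement name different time points for the same two analytes. Analysis tables are normally programmed from the methods section. A programmer who follows this list would build a Day 0 table for which no assay is planned, and would have no instruction to build the pre-booster table.

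At stake is the description of PT and FHA antibody levels just before the booster in Group 4, the only 3+1 group. For Group 3, the other PCV13 group, SAP 5.1.3 (Objective 3) does itemise pre-booster summaries. The two PCV13 groups would then be reported differently at that time point.

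**Working it through.** No power, alpha or sample-size figure is involved, so the check sets the sources side by side for PT and FHA in Group 4.

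| Sample | Timing | Assay planned (protocol Table 9.3) | Endpoint 6 (protocol 9.2.2.1, SAP 4.2.1.1) | SAP 5.1.4 lead-in | SAP 5.1.4 list |
|---|---|---|---|---|---|
| BL0001 | Day 0 | No | No | No | **Yes** |
| BL0002 | 30 days after Dose 3 | No | No | No | No |
| BL0003 | Before Dose 4 | Yes | Yes | Yes | **No** |
| BL0004 | 30 days after Dose 4 | Yes | Yes | Yes | Yes |

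The list departs from the other sources in exactly two cells: it adds BL0001 and drops BL0003.

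**Could Day 0 be deliberate?** Three observations speak against it.

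1. In Groups 1 to 3 the Day 0 values have a use. SAP 4.4.2.6 takes the pre-primary concentration as the baseline for the seroresponse after the infant doses. The same section defines no post-primary pertussis seroresponse for Group 4. There it covers only the booster: "for Group 4, before and 30 days after the booster dose (Dose 4), Pertussis vaccine seroresponse for anti-PT and anti-FHA is defined as", with the pre-booster concentration as comparator.
2. The two Day 0 lines are worded identically under Objective 3 (Groups 1, 2 and 3) in SAP 5.1.3, where they match Tables 9.1 and 9.2. Carry-over from there is the likely explanation, though it is an inference.
3. SAP 5.7 records departures from the protocol down to single thresholds: "Finally, several analysis cut-offs for some concentrations have been considered in addition to the one already defined in the protocol". Some of those additions concern objective 6. No change of pertussis time point is among them.

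**Size.**

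- Planned Day 0 PT and FHA testing: 716 + 716 + 110 = 1542 enrolled subjects in Groups 1 to 3, and 0 of 110 enrolled in Group 4 (88 planned evaluable).
- Pre-booster analytes itemised: endpoint 6 names 2 (PT, FHA); SAP 5.1.4 lists 0 of those 2.
- Hexavalent analytes assayed at BL0003 in Group 4 (Table 9.3): PRP 1 + HBsAg 1 + PT 1 + FHA 1 + polio 3 + diphtheria 1 + tetanus 1 = 9, so 9 − 2 = 7 besides PT and FHA.

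**The case against.** The strongest reply is that this is a clerical slip in one bullet, surrounded by correct text. The lead-in, SAP endpoint 6 and SAP 4.4.2.6 all point to the pre-booster sample. Because the Group 4 seroresponse needs the BL0003 values, those values must be in the analysis dataset in any case. A Day 0 table would come out empty and expose the error; it could not yield a plausible wrong result. The objective is descriptive, and the sample-size sections of both documents say that Group 3 and Group 4 data are not meant for hypothesis testing. The silence of SAP 5.7 fits a slip as well as it fits anything else, since that section records intended changes.

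Most of this stands, and it bounds the consequence. It does not remove the inconsistency. An empty Day 0 table would reveal that something is wrong, but it would not by itself produce the missing pre-booster summary. Whether the table shells already have the right time point cannot be seen from these documents.

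It is also fair to say that the 7 other hexavalent analytes are a separate matter. The broad lead-in with only PT and FHA itemised before the booster is already present in protocol endpoint 6 and did not arise in SAP 5.1.4.

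**Conclusion.** The point holds. As written, SAP 5.1.4 specifies a Group 4 Day 0 summary of PT and FHA with planned data in 0 of 110 subjects, and itemises neither of the two pre-booster summaries that both documents define as part of secondary endpoint 6. It should be corrected, but the effect is small. No hypothesis test, power or alpha depends on it, the primary objective and secondary objective 1 are untouched, and the pertussis booster seroresponse remains computable from BL0003 and BL0004.

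The conclusion rests on reading Table 9.3 as the complete assay plan for Group 4. Endpoint 6 independently supports that reading, since it has no Day 0 pertussis item either.

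**What to change.** In SAP 5.1.4, Objective 6, replace the Day 0 time point for the PT and FHA geometric means and 95% CIs with the pre-booster sample (BL0003, Visit 5). The cost is one line and the matching table. Table 9.3 already plans pertussis testing at that sample, so no added blood draw or assay is needed.

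If Day 0 testing in Group 4 was in fact intended, add it to Table 9.3 and to endpoint 6, record it in SAP 5.7, and still list the pre-booster item.

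As an optional clarification, state whether pre-booster summaries are also wanted for the 7 other hexavalent analytes assayed at BL0003. That would add summaries for 7 analytes, again without new assays.
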